4.14.1. Additional Analyses of All Cause Mortality

Deaths will be analyzed on the basis of the adjudicated cause of death which will be categorized into CV death and non-CV death. Deaths with an undetermined cause will be included in CV deaths for analysis purposes. Time-to-event analyses will be performed for all deaths as well as for each adjudicated cause of death (CV death versus non-CV death and the subcategories under CV death). Incidence rates per 100 person-years of follow-up will be calculated for each type of death for each treatment group. The NNT statistic will not be provided for these analyses. These analyses will be performed using the ITT population.

A by-patient listing of all deaths and the adjudicated outcome will be provided.

4.14.2. Additional Analyses of MI Endpoint

The additional analyses of the MI endpoint will be performed using the ITT population.

4.14.2.1. Analyses of Classifications MI Endpoint

4.14.2.1.1. Universal MI Definition

For each MI event, the adjudicators will classify the MI type using the universal MI definition (Thygesen et al. 2007) as follows:

Type 1: Spontaneous MI related to ischemia due to a primary coronary event such as plaque erosion and/or rupture, fissuring, or dissection

Type 2: MI secondary to ischemia due to either increased oxygen demand or decreased supply, for example, coronary artery spasm, coronary embolism, anemia, arrhythmias, hypertension, or hypotension

Type 3: Sudden unexpected cardiac death, including cardiac arrest, often with symptoms suggestive of myocardial ischemia, accompanied by presumably new ST elevation, or new Left Bundle Branch Block, or evidence of fresh thrombus in a coronary artery by angiography and/or at autopsy, but death occurring before blood samples could be obtained, or at a time before the appearance of cardiac biomarkers in the blood

Type 4: MI associated with PCI or MI associated with stent thrombosis as documented by angiography or at autopsy

Type 5: MI associated with CABG

Each type of MI (using the universal MI definition) will be further summarized in categories of multiples (1-2X, 2-3X, 3-5X, 5-10X, and >10X) of the 99th percentile of the upper reference limit (URL) of cardiac biomarkers creatine kinase-MB (CK-MB) or troponin, and compared between treatment groups.

4.14.2.1.2. Other Classifications of Myocardial Infarction

The adjudicators will also classify MI type as STEMI vs NSTEMI and by subtypes of MI (Spontaneous, Periprocedural [PCI or CABG related], or Silent). Myocardial infarction types will be summarized using number and proportion of patients for both treatment groups using these different classification schemes. For these analyses, the denominator will be the total number of patients having an MI. If a patient has >1 MI, only the first MI will be included in the analysis.

4.14.2.2. Subgroup Analysis of Nonfatal Myocardial Infarction Endpoint

For subgroup analyses all adjudicated nonfatal MI outcomes will be included, and the analyses will be performed for the ITT population. The potentially clinically relevant baseline risk factors and medication use for exploratory subgroup analyses for the MI events will include: prior MI, prior hospitalization for unstable angina, prior coronary revascularization, current smoker, hypertension, hyperlipidemia, aspirin use, beta-blocker use, calcium channel blocker use, ACE inhibitor or angiotensin receptor blocker use, diuretic use, and antithrombotic use (excluding aspirin).

The risk-adjusted analysis will be performed using these risk factors, medication use, the prespecified subgroups (Section 4.13.3), and a multivariate proportional hazards model. The risk factors and medication use remaining in the final model plus the pre-specified subgroup variables will be used for subgroup analyses.

4.14.2.3. Analysis of Fatal Myocardial Infarction Endpoint

A fatal MI is defined as an MI event that resulted in death within 30 days. Time-to-event analysis (Section 4.3.4) will be performed for all adjudicated fatal MI outcomes using the ITT population. Subgroup analyses will also be performed if there are enough cases of fatal MIs (Section 4.3.5 and Section 4.13.3).

4.14.3. Additional Analyses of All Stroke Endpoint

Time-to-event analyses will be performed for each subtype of stroke (hemorrhagic, ischemic, or unknown) in the ITT and PP populations. Incidence rates per 100 person-years of follow-up will be calculated for each type of stroke for each treatment group. The NNT statistic will not be provided for these analyses.

Stroke disability, as measured using the modified Rankin scale (Farrell et al. 1991), will be assessed at approximately 30 days after the diagnosis. The number of patients in each of the following categories of the scale will be summarized and compared between treatment groups using a Chi-square test Fisher's exact test:

- 0: No symptoms at all
- 1: No significant disability despite symptoms (Able to carry out all usual activities)
- 2: Slight disability
- 3: Moderate disability (Requiring some help but able to walk without assistance)
- 4: Moderate to severe disability (Unable to walk without assistance and unable to attend to own bodily needs without assistance)
- 5: Severe disability (Bedridden, incontinent and requiring constant nursing care and attention)
- 6: Death.

4.14.4. Subgroup Analysis of Nonfatal Stroke Endpoint

For subgroup analyses all adjudicated nonfatal stroke outcomes will be included, and the analyses will be performed for the ITT population. The potentially clinically relevant baseline risk factors and medication use for exploratory subgroup analyses for the stroke events will include: prior MI, prior hospitalization for unstable angina, prior history of stroke or TIA, carotid or other artery disease, current smoker, alcohol abuse, hypertension, hyperlipidemia, aspirin use, beta-blocker use, calcium channel blocker use, ACE inhibitor or angiotensin receptor blocker use, diuretic use, history of atrial fibrillation, and antithrombotic use (excluding aspirin).

The risk-adjusted analysis will be performed using these risk factors and the prespecified subgroups, and a multivariate proportional hazards model. The risk factors and medication use remaining in the final model plus the prespecified subgroup variables will be used for subgroup analyses.

4.14.5. Analysis of Fatal Stroke Endpoint

A fatal stroke is defined as a stroke event that resulted in death within 30 days. Time-to-event analysis (Section 4.3.4) will be performed for all adjudicated fatal stroke outcomes using the ITT population. Subgroup analyses will also be performed if there are enough cases of fatal strokes (Section 4.3.5 and Section 4.13.3).

4.14.6. Exploratory Analyses: Analyses of Multiple Cardiovascular Events

A patient may experience more than one CV event during the course of the study. For example, a patient may be hospitalized for an unstable angina and later experience a nonfatal MI which

may be followed by death from a CV cause, or a patient may experience 3 nonfatal MIs or 2 nonfatal strokes. In each case, the patients will be considered as having multiple CV events. To assess the effects of dulaglutide on multiple CV events compared to placebo, analyses accounting for multiple CV events will be performed. The analyses will be performed separately for the composite primary endpoint; acute coronary syndrome (ACS) events which include nonfatal MI and hospitalization for unstable angina; MIs; strokes; MACE (composite of nonfatal MI, stroke and CV death) and heart failures requiring hospitalization. In each of these analyses, a patient who experiences multiple events of the endpoint will be considered as having recurrent events of the endpoint. The conditional Gap Time model of Prentice, Williams, and Peterson (PWP-GT) (Prentice et al. 1981) will be used to analyze recurrent CV events. The hazard ratio with 95% CI will be reported for time to the first event, second event, etc. The mean time between successive events will also be reported by treatment group. Baseline characteristics will be compared between groups of patients with no event, only one event, and multiple events (2 or more) regardless of treatment assignment and between treatments within each group. Counts and proportion for categorical variables will be compared using a Chi-square or Fisher's exact test and means for continuous variables will be compared using ANOVA.

4.14.7. Exploratory Analyses: Analysis of Nonfatal Cardiovascular Events with Competing Risk of Death

The composite endpoint of nonfatal CV events (that is, the first occurrence of nonfatal MI, nonfatal stroke, hospitalization for unstable angina, HF requiring hospitalization or an urgent HF visit, or coronary, carotid, or peripheral revascularization), will be analyzed taking into account the competing risk of death. The competing risk model of Fine and Gray will be used (Fine and Gray 1999). Covariates of interest include treatment and the baseline CV risk factors listed in Section 4.13.3.

4.15. Additional Measures

Additional measures include:

- Change from baseline in:
 - hemoglobin A1c levels
 - weight
 - waist/hip ratio
 - cognitive function as measured by the MoCA and the DSST
 - erectile dysfunction as measured by the IIEF
- Time to first occurrence of (after randomization):
 - composite endpoint of death from CV causes, nonfatal MI, nonfatal stroke, or hospitalization for unstable angina

- coronary, carotid, or peripheral revascularization, individually and compositely
- any hospitalization
- Incidence of:
 - any fracture
 - development of cholelithiasis

An independent CEC will adjudicate coronary, carotid, and peripheral revascularizations. Detailed event definitions and specifics regarding endpoint determination are provided in the CEC Charter.

- A **coronary, carotid, or peripheral arterial revascularization** procedure will be defined as a catheter based or open surgical procedure designed to improve myocardial, carotid, or peripheral arterial blood flow. Insertion of a guidewire through a coronary guide catheter into a coronary artery or bypass graft for the purpose of PCI is considered intention for PCI. The intention to perform percutaneous peripheral arterial intervention is denoted by the insertion of a guidewire through a guide catheter into a peripheral artery.
- A **hospitalization** will be defined as a hospital admission (including admission to a chest pain observation unit) or a visit to an emergency department that results in a stay >24 hours.
- A **fracture** will be defined as a clinically or radiologically apparent fracture of any bone.
- **Development of Cholelithiasis** will be defined as any new diagnosis of cholelithiasis after randomization, as evidenced on an imaging examination (for example, ultrasound or computerized tomography scan).

4.15.1. Analyses of HbA1c, Weight, and Waist/Hip Ratio

For HbA1c, weight, and waist/hip ratio, an MMRM analysis for the change from baseline to each visit will be performed for the ITT population (Section 4.3.2). Baseline for HbA1c and weight will be Visit 1 (Screening). A correction factor will be used to standardize the HbA1c values reported depending on whether the measurement method was IFCC or DCCT.

4.15.2. Analyses of Cognitive Function and Erectile Dysfunction

Cognitive function will be assessed in all randomized patients using the MoCA instrument and the DSST at baseline (Visit 3) and after 24, and 60 months of treatment and at the final visit.

The MoCA is a cognitive screening test designed to detect mild cognitive impairment (Nasreddine et al. 2005). It assesses different cognitive domains: attention and concentration, executive functions, memory, language, visuoconstructional skills, conceptual thinking,

calculations, and orientation. It will take approximately 10 minutes to complete the test. The total possible score is 30 points; a score of 26 or above is considered normal.

The DSST is an attention-demanding psychomotor component of the Wechsler Adult Intelligence Scale (Kuo et al. 2007). The patient is given a symbol-digit code in which each of the digits 1 through 9 is paired with a different symbol. Below the code, a series of symbols selected from those in the code are presented in an irregular order. The patient is instructed to draw the symbol that matches the number and to complete as many correct symbols as possible within a 120-second test period. The DSST score is the number of correct symbol-number matches. The number of matches attempted will also be recorded.

Analyses of the last score for the MoCA and the DSST, and visit-specific analyses will be performed using MMRM (Section 4.3.2) for each of these continuous test scores. The analysis will be based on change from baseline. Patients will be required to have a baseline and at least one post-baseline score to be included in these analyses.

The MoCA score is a continuous variable with a range of [0, 30]. It will also be analyzed as a categorical variable using the categories: below the threshold for normal cognitive function (that is, mild cognitive dysfunction, MoCA score <23 for Korea and MoCA score <26 for all other countries), and above the evaluation threshold (that is, normal cognitive function, MoCA score \geq 23 for Korea and MoCA score \geq 26 for all other countries). The number and proportion of patients in each category at each visit will be compared between treatment group using a Chi-square test or Fisher's exact test.

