#### **7.1.4. Treatment Period (Visit 4 and Beyond)**

Visit 4 will occur 2 weeks, Visit 5 at 3 months, and Visit 6 at 6 months after randomization; subsequent study visits will occur approximately every 6 months thereafter until study closure. Study drug dispensing should occur approximately every 3 months after randomization. At the investigator's discretion, and after confirming sufficient non-expiring study drug is available on site, a 6-month supply of study drug may be dispensed to maintain a patient's compliance with study drug.

Study procedures are those outlined in the Study Schedule ([Attachment 1](#)).

At all post-randomization visits, concomitant medications, AEs, and adherence to study drug and lifestyle interventions will be reviewed. New endpoint events (for example, CV events) will be collected and recorded. Vital signs will be measured. Self-monitored blood glucose testing supplies will be dispensed. Injection instructions will be reviewed, if needed.

Electrocardiograms will be recorded and weight measurements will be obtained every 12 months and at the final visit. Height and waist and hip circumference will be measured every 24 months and at the final visit. Samples for laboratory tests will be collected as outlined in the Study Schedule ([Attachment 1](#)). Laboratory samples that need to be drawn fasting should be drawn after an 8-hour fasting period. Calcitonin will be measured by the central laboratory. All other laboratory tests will be performed locally, including additional pregnancy tests for women of childbearing potential. Patients will be administered the cognitive function tests (that is, MoCA and DSST) and men will complete the erectile function questionnaire (that is, IIEF) at Visits 3, 9, 15, and the final visit as scheduled ([Attachment 1](#)).

Management of glycemic control will be at the discretion of the study investigator and will be informed by current guidelines and/or local standards of medical care (Section 9.5.2). The investigator may increase or reduce the dose of existing glucose-lowering therapies, or add or remove other glucose-lowering therapies (with the exception of a GLP-1 receptor agonist or pramlintide) to maintain acceptable glycemia control and to reduce hypoglycemic episodes. Either the study investigator or the patient's usual physician(s) will manage other CV risk factors and comorbid conditions (depending on local arrangements).

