#### **12.2.10. Analysis for the Additional Objectives**

For HbA1c, weight, and waist/hip ratio, an ANCOVA for the change from baseline to each visit and to endpoint (last available observation) will be performed for the ITT population. The model includes treatment as a fixed effect and the baseline value as a covariate. Missing endpoints will be imputed using a multiple imputation procedure on available postbaseline values of the variable. If there are no data after the date of randomization, the endpoint will be considered missing. The baseline data will not be used as an endpoint.

Time-to-event analyses will be performed for each of the following endpoints: the composite endpoint of death from CV causes, nonfatal MI, nonfatal stroke, or hospitalization for unstable angina; the composite endpoint of coronary, carotid, or peripheral revascularization and each of the components; and any hospitalization. A Cox proportional hazards regression model for the time to the first occurrence of the event, with treatment as a fixed effect will be performed for the ITT population.

Frequency counts and percentages of patients with fractures and patients, who developed cholelithiasis, will be presented for each treatment group and compared across treatment groups using Chi-square tests or Fisher's exact tests.

Cognitive function will be assessed in patients using the MoCA instrument and the DSST.

The DSST score is the number of correct number-symbol matches. The number attempted will also be recorded. Analyses of the last score and visit-specific analyses will be performed using ANCOVA for each continuous test measurement. The analysis will be based on change from baseline. Patients will be required to have a baseline and at least 1 postbaseline score to be included in these analyses.

The MoCA score is a continuous variable with a range of [0, 30]. It will be analyzed as a categorical variable using the categories: below the threshold for normal cognitive function (that is, mild cognitive dysfunction, MoCA score <26), and above the evaluation threshold (that is, normal cognitive function, MoCA score  $\geq$ 26).

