4.3.2. Post-Baseline Analyses of Continuous Variables

For each continuous response variable, visit-specific analyses will be performed for the visits where the variable was scheduled to be measured. If a patient has no post-baseline measurements of a variable, the patient will not be included in the visit-specific analyses of that variable. Analyses of change and percent change from baseline to specific visits will have the same requirements plus the additional constraint that the patient has a baseline measurement of the variable.

The default analysis model for continuous response variables expected to be normally distributed will be a mixed-effects model for repeated measures (MMRM) using restricted maximum

likelihood (REML). The MMRM model will be used to analyze changes from baseline with the baseline value as the covariate. The model will include fixed effects for treatment, visit, treatment-by-visit interaction, the baseline as a covariate, and the patient as a random effect. An unstructured covariance structure will be used to model the within-patient errors. This analysis includes visits where the continuous response variable was scheduled to be measured.

If this analysis fails to converge, the following covariance structures will be tested in order:

- toeplitz with heterogeneity
- autoregressive with heterogeneity, by visit
- compound symmetry with heterogeneous variances, by visit
- toeplitz,
- autoregressive
- compound symmetry without heterogeneous variances, by visit

The first covariance structure that converges will be used. The Kenward-Roger approximation will be used to estimate denominator degrees of freedom. Significance tests will be based on least-squares mean (LS Mean) using Type III sum of squares.

Summary statistics will include sample size, mean, SD, median, 10th and 90th percentiles for both the actual and the change from baseline measurements. Least-squares mean (LS Mean) and standard error (SE) derived from the model will also be displayed for the change from baseline measurement. Treatment comparisons will be displayed showing the treatment difference LS Mean and the 95% confidence limits along with the p-value.

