4.3.3. Post-baseline Analyses of Categorical Variables

Categorical variables will be compared between treatment groups using the Pearson chi-square test if the expected count is at least 5 in at least 80% of the cells; otherwise, Fisher's exact test will be used. Summaries for these variables will include the between-treatment p-value and the

descriptive statistics: number and proportion of patients. For post-baseline outcome variables, the relative risk estimate and the associated 95% CI will be provided, if there are at least 10 patients with the outcome.

If the categorical variable is associated with a scheduled post-baseline measurement, then a patient must have a measurement of the variable to be included. However, when the categorical variable is the occurrence of an event (yes/no), such as development of an adverse event (AE), then all randomized patients will be included in the analysis.

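### The supplementary MoCA below/above-threshold comparison leaves out the Visit 3 score; the test is valid, but adjusting for baseline would make it more precise at almost no cost.

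*SAP*

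**What the plan says.** MoCA is given "at Visits 3, 9, 15, and the final visit as scheduled" (Protocol 7.1.4), so a baseline score is planned for every randomized patient, with follow-up at 24 months, 60 months and study end.

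SAP 4.15.2 handles the score in two ways.

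- **Continuous.** Change from baseline is analysed by the MMRM of SAP 4.3.2, where "The MMRM model will be used to analyze changes from baseline with the baseline value as the covariate". On who enters: "Patients will be required to have a baseline and at least one post-baseline score to be included in these analyses".
- **Categorical, in addition.** Patients are classed as below or above the threshold (below 23 in Korea, below 26 elsewhere), and numbers and proportions "in each category at each visit will be compared between treatment group" by chi-square or Fisher's exact test. No baseline term appears.

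The categorical test follows the default in SAP 4.3.3. That section asks only for a value at the visit: "then a patient must have a measurement of the variable to be included". SAP 4.3.1 restricts covariate adjustment in the study report to baseline factors that differ between the arms both clinically and statistically, so an adjusted version would not arise by default.

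Protocol 12.2.10 says of the MoCA score: "It will be analyzed as a categorical variable using the categories" below 26 and 26 or above.

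**The concern.** A patient's MoCA before treatment is likely to be a strong predictor of being below the threshold two or five years later. A chi-square test treats all of that predictable between-patient variation as noise. The baseline score is already scheduled, and the MMRM of the same instrument already uses it, so the category comparison gives up precision that the trial has the data to recover.

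What is at stake is small: the width of the interval, and the power, for the threshold form of one additional objective. That form is the one a clinician can read most directly, which is why it is worth estimating as well as the data allow.

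**Working it through.** **No figure to reproduce.** The documents give no MoCA mean, SD, impaired proportion, correlation or power. From the documents: about 9600 patients randomized 1:1 (4800 per arm), two-sided alpha 0.05, cut-off 26 (23 in Korea). Assumed: correlation ρ between baseline and follow-up, and proportion impaired p.

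**Step 1. Information gained.** Take the two scores as bivariate normal with correlation ρ. If R² is the share of the variance of the below-threshold indicator explained by the baseline score, adjustment multiplies the variance of the treatment contrast by about 1 − R². The information ratio is then 1/(1 − R²) and the standard error ratio √(1 − R²). At p = 50%, R² = (2/π)·arcsin(ρ²). For ρ = 0.6: (2/π)·arcsin(0.36) = 0.234, information ratio 1/0.766 = 1.31, standard error ratio √0.766 = 0.875.

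| ρ | R² (p = 50%) | Information ratio | Standard error smaller by | Simulated information ratio |
|---|---|---|---|---|
| 0.4 | 0.102 | 1.11 | 5% | 1.10 |
| 0.5 | 0.161 | 1.19 | 8% | 1.16 |
| 0.6 | 0.234 | 1.31 | 13% | 1.29 |
| 0.7 | 0.326 | 1.48 | 18% | 1.48 |

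The last column is the squared ratio of mean z statistics, logistic regression with baseline against the unadjusted test. Scores were rounded and capped at 30, with assumed mean 25.5, SD 3.3, threshold 26 and a shift of 0.1 SD. A repeat run gave 1.10, 1.19, 1.27 and 1.48. With p = 20% instead of 50%, R² is 0.083 to 0.288 over the same ρ.

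**Step 2. Error rate.** Under no effect (p = 50%, ρ = 0.6, 4000 per arm, 1000 replicates), rejection was 5.2% for chi-square and 5.5% for the adjusted model. The Monte Carlo standard error is √(0.05 × 0.95/1000) = 0.7 points, so both agree with 5%.

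**Step 3. Power at a fixed difference.** The shift in Step 1 gives about 50% against 46% impaired. Then z = 0.04/√[(0.50 × 0.50 + 0.46 × 0.54)/n] = 0.04/√(0.4984/n). Power is Φ(z − 1.96) unadjusted and Φ(z·√IR − 1.96) adjusted, where IR is the information ratio.

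| n per arm | z | Chi-square | Adjusted, IR 1.10 | Adjusted, IR 1.48 |
|---|---|---|---|---|
| 1500 | 2.19 | 59% | 63% | 76% |
| 3000 | 3.10 | 87% | 90% | 97% |
| 4000 | 3.58 | 95% | 96% | 99% |
| 4800 | 3.93 | 97.5% | 98.5% | 99.8% |

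**Step 4. Power where chi-square has 80%.** With 4800 per arm that is a difference of 2.2 to 2.9 percentage points for p from 20 to 50%. Adjusting for the score raises power to between 83% and 93% for ρ from 0.4 to 0.7. Simulation at p = 35%, ρ = 0.6 and 4000 per arm gave 78% unadjusted and 90% adjusted for the score. Adjusting for the baseline category alone gave 86%, so the continuous score is the better covariate.

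**The case against.** The case for leaving the text alone is reasonable. The trial's main MoCA comparison already uses baseline. The category is a supplementary view of an additional measure, follows the SAP's own default, has the right error rate, and lies outside the multiplicity scheme. It also keeps patients who have a follow-up score but no baseline, whom an adjusted model would drop. All of that stands. It limits the importance of the point without removing the loss of precision.

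Four stronger readings are tempting, and the documents do not support them.

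- *The trial ignores baseline cognition.* It does not: the MMRM in the same SAP section adjusts for it.
- *The category is the only planned MoCA analysis.* Protocol 12.2.10 read alone suggests this. But Protocol 10.1.3 lists change from baseline in MoCA as a measure, Protocol 12.2.1 gives baseline-adjusted models for continuous changes and lets the SAP alter non-principal methods, and the SAP revision history (Version 3) names MMRM for MoCA.
- *The unadjusted test mostly measures baseline status.* Information ratios of 1.10 to 1.48 put the explained share at 1 − 1/1.10 = 9% to 1 − 1/1.48 = 32%. Randomization keeps the comparison unbiased whatever that share is.
- *Power would rise from about 60% to 75%.* That needs roughly 1500 patients per arm, a 4-point difference and a correlation of 0.7. At the same difference with 4800 per arm, chi-square power is already about 97%.

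**Conclusion.** The point holds as a minor matter of efficiency. The threshold comparison is valid but leaves out a covariate that the trial plans to collect on everyone. Adjustment would be worth about 10 to 48% more information for correlations of 0.4 to 0.7. What that buys in power varies with the true difference and the number tested: about 1 to 2 points where chi-square power is near 97%, and 3 to 13 points where it is 80%.

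The direction of the gain is the same at every correlation and impaired proportion tried; its size rests on those assumed values. Nothing in the primary analysis or the alpha-controlled secondary analyses is affected.

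**What to change.** In SAP 4.15.2, before unblinding:

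- Make the between-group comparison of the MoCA category at each visit a logistic regression on treatment and baseline MoCA score. Express baseline relative to the local cut-off (23 in Korea, 26 elsewhere), or add a Korea term. A raw score alone would give the same baseline value a different meaning in Korea.
- Report the standardized risk difference and the odds ratio, each with a 95% CI. The risk difference is the one to set beside the raw percentages, because the adjusted odds ratio is conditional on baseline.
- State that this is a prespecified exception to the covariate rule in SAP 4.3.1.
- Keep the counts, percentages and chi-square or Fisher result as description, on all patients measured at the visit.
- State the rule for a missing baseline. MoCA is not scheduled before Visit 3, so there is no earlier score to fall back on. Either those patients leave the adjusted model, as they already leave the continuous analysis, or a missing-baseline indicator keeps them in.

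The cost is SAP text and a short program, with no new data or visits. The one drawback is the possible loss of patients without a baseline score, which the indicator avoids.
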